8.10 POST-PROCEDURE CARE

Following the angiogram and procedure, the subjects will be asked to lie flat with a pressure bandage over the groin puncture site according to the local standard of care (e.g., assess for bleeding, hematoma, pedal pulses). A post-implant carotid duplex imaging study is required prior to discharge. The subject will be monitored closely for significant change in status (peri-procedural adverse events).

Implanted subjects should be monitored in an intensive care or intermediate care unit; with emphasis on meticulous blood pressure monitoring over the first 12 hours for recognition and/or prevention of severe hypotension (symptomatic drop in BP below 90/50) or severe hypertension (rise in BP above 180/100 mmHg with or without symptoms). If blood pressure drops below 90/50 with clinical symptoms or the subject has symptoms with a relative drop from baseline pressure due to past compensatory changes, then aggressive rescue (may include pressors, fluids, placement in trendelenburg position, withdrawal of blood pressure medications, etc.) should be provided to increase blood pressure to a point where the symptoms are alleviated. Blood pressure medications can be withdrawn if there is an abrupt drop in blood pressure from baseline, and should be documented as an adverse event and logged in the medication log. Aggressive use of protamine sulfate to antagonize the total dose of heparin should be avoided due to risk of implant thrombosis. Take vital signs once an hour for three (3) hours and enter data in the post-procedure iCRF. Standard post-procedure labs should be taken prior to discharge. These labs should include CBC, Chem 7, and Hematologic labs.

Prior to release from the hospital the subject's lying and standing bedside blood pressure should be measured and analyzed for orthostatic changes. In addition, the subject must be ambulatory, without dizziness or other symptoms.

If a new neurological deficit or a significant change in neurological status is determined using the NIHSS during post-procedure monitoring, assess for intracranial thrombus or hemorrhage using CT scan or MRI, if deemed appropriate by the Investigator under standard of care, and treat accordingly.

Body temperature $>38^{\circ}\text{C}$ should be investigated, and testing performed per the standard of medical care (e.g., blood cultures, urinalysis, chest X-ray, phlebitis source), to allow appropriate treatment to be implemented.

8.11 SUBJECT DISCHARGE

On the day of discharge, clinical and neurological assessment of the subject is completed. Duplex imaging is done to visualize the carotid sinus and to assess for complications. Office cuff blood pressure should be taken and documented on the discharge iCRF. Orthostatic blood pressure measurement and orthostatic pulse assessments should be taken (sitting and standing). Assessment for any new or unresolved adverse events will be made and any changes in medication regimen will be recorded.

8.12 7-DAY FOLLOW-UP VISIT (+2 / -3 DAYS)

During the 7-Day follow-up visit, clinical assessment of the subject and evaluation of neurological symptoms will be performed by the study team. Office cuff blood pressure will be taken and assessment of the subject diary will be reviewed. A six minute walk test will be done following the March 2002 ATS Statement: Guidelines for the Six-Minute Walk Test, and orthostatic assessment should be done following this test. Orthostatic blood pressure measurement and orthostatic pulse assessments should be taken (sitting and standing). The neurological examinations are classified by NIHSS. Duplex imaging is done to visual carotid sinus and to assess for complications. Assessment for any new or unresolved adverse events will be made and any changes in medication regimen will be recorded.

8.13 30-DAY FOLLOW-UP VISIT (+7 / -7 DAYS)

During the 30-Day follow-up visit, clinical assessment of the subject and evaluation of neurological symptoms will be performed by the study team. Duplex imaging is done to visualize the carotid sinus and to assess for complications. Office cuff blood pressure will be taken and assessment of the subject diary will be reviewed. A six minute walk test will be done following the March 2002 ATS Statement: Guidelines for the Six-Minute Walk Test and orthostatic assessment should be done following this test. Orthostatic blood pressure measurement and orthostatic pulse assessments should be taken (sitting and standing). The neurological examinations are classified by NIHSS. Assessment for any new or unresolved adverse events will be made and any changes in medication regimen will be recorded.

8.14 90-DAY FOLLOW-UP VISIT (+14 / -14 DAYS)

During the 90-Day follow-up visit, clinical assessment of the subject and evaluation of neurological symptoms will be performed by the study team. Office cuff blood pressure will

be taken and assessment of the subject diary will be reviewed. 24-hour ambulatory blood pressure monitoring will be assessed. The neurological examinations are classified by NIHSS. Assessment for any new or unresolved adverse events will be made and any changes in medication regimen will be recorded.

8.15 180-DAY FOLLOW-UP VISIT (+14 / -14 DAYS)

During the 180-Day follow-up visit, clinical assessment of the subject and evaluation of neurological symptoms will be performed by the study team. Office cuff blood pressure will be taken and assessment of the subject diary will be reviewed. 24-hour ambulatory blood pressure monitoring will be assessed. The neurological examinations are classified by NIHSS. Duplex imaging is done to visualize the sinus and to assess for complications. Assess for any new or unresolved adverse events and record any changes in medication regimen. Assessment for any new or unresolved adverse events will be made and any changes in medication regimen will be recorded.

8.16 365-DAY FOLLOW-UP VISIT (+14 / -14 DAYS)

During the 365-Day follow-up visit, clinical assessment of the subject and evaluation of neurological symptoms will be performed by the study team. Office cuff blood pressure will be taken. The neurological examinations are classified by NIHSS. Assessment for any new or unresolved adverse events will be made and any changes in medication regimen will be recorded.

8.17 LONG TERM FOLLOW-UP VISITS - 18, 24, 30, AND 36-MONTH FOLLOW-UP VISIT (+14 / -14 DAYS)

During the long term follow-up visits after the angiogram/implantation procedure, clinical assessment of the subject and evaluation of neurological symptoms will be performed by the study team. Office cuff blood pressure will be taken. The neurological examinations are classified by NIHSS. Assessment for any new or unresolved adverse events will be made and any changes in medication regimen will be recorded.

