--	-------------------------------------------------------------------------------------------------------------------------------------------------------------------------------------------------------------------------------------------------------------------------------------------------------------------------------------------------------------------------------------------------------------------------------------------------------------------------------

STUDY ENROLLMENT	
This study will be enrolled based on the following matrix with review of Data Safety Monitoring Board (DSMB) and FDA:
 
Unilateral study safety design:
  
Subject 1
 
•DSMB review of 7-day data 
Subject 2-5
 
•DSMB review of 7-day data 
Subject 6-10
 
•DSMB review of 7-day data of subjects 6-10•Data submitted to FDA for approval of dose escalation to bilateral implantation or continued unilateral implantation of subjects 11-20 
Following enrollment of the initial 10 subjects, based on DSMB review of available data, a determination will be made on whether the safety of the MobiusHD is adequate to support bilateral placement. If the DSMB determines that bilateral treatment is warranted, an interim report with all available clinical data will be submitted to FDA with a request for initiation of bilateral treatment in the remaining 10 study subjects.
 
Bilateral study design: (if approved by DSMB and FDA)
  
Subject 11
 
•DSMB review of 7-day data 
Subject 12-15
 
•DSMB review of 7-day data 
Subject 16-20
 
•DSMB review of 7-day data of subject 16-20

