6.2 EXCLUSION CRITERIA

Candidates will be ineligible for enrollment in the study if any of the following conditions are identified at the screening or baseline visits:

Baseline Screening Visit 1 – (Day 0 – 14) – Assessed on Day 14

1. Known or clinically suspected baroreflex failure or autonomic neuropathy;
2. Hypertension secondary to an identifiable and treatable cause other than sleep apnea (e.g., hyperaldosteronism, renal artery stenosis, pheochromocytoma, Cushing's disease, coarctation of the aorta, hyperparathyroidism and intracranial tumor);
3. Treatable cause of resistant hypertension including, but not limited to, improper BP measurement, volume overload and pseudotolerance (excessive sodium intake, volume retention from kidney disease, inadequate diuretic therapy), drug-induced or other causes (non-adherence, inadequate doses, inappropriate combinations, NSAIDs, COX-2 inhibitors, cocaine, amphetamines, or other drugs, sympathomimetics, oral contraceptives (confirmed cause of resistant hypertension), adrenal steroids, cyclosporine, and tacrolimus, erythropoietin, licorice (including some chewing tobacco), ephedra, ma haung, bitter orange); and excessive alcohol intake;
4. Arm circumference greater than 46 cm and/or BMI \geq 40;
5. Chronic atrial fibrillation;
6. Vulnerable plaque or ulceration of any size in the carotid artery or aortic arch;
7. History of bleeding complications with dual anti-platelet therapy in the past or has known uncorrectable bleeding diathesis;
8. Current use of additional anticoagulation therapy. Examples include vitamin K antagonists like warfarin, direct thrombin inhibitors, direct factor Xa inhibitors, thrombin IIa inhibitors like apixaban, rivaroxaban, dabigatran and etexilate;
9. Peptic ulcer disease with documented active ulcer or bleeding within the last year;
10. History of allergy to contrast dye that cannot be managed medically;
11. History of orthostatic hypotension;
12. History of syncope within the last six (6) months;
13. History of myocardial infarction or unstable angina within the past three (3) months;
14. History of cerebral vascular accident (stroke or TIA) within the past year;
15. Severe chronic kidney disease (calculated GFR < 45 ml/min);
16. Prior surgery, radiation, or endovascular stent placement in either carotid region;

17. Clinically significant structural valvular cardiac disease;

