8.4 SELECTION AND SCREENING OF SUBJECTS

Prior to subject participation in this study, the study team must obtain written IRB/EC approval for the Protocol and the ICF. The study population for this clinical trial will be comprised of adult patients who have been diagnosed with stage 2 resistant hypertension. In addition, these patients must satisfy the inclusion and exclusion criteria. The trial will prospectively enroll up to 20 subjects. Patients presenting with stage 2 resistant hypertension must be on a minimum of three (3) anti-hypertensive medications. Clinical site personnel will review the patient's medical history for eligibility. Potential candidates will be fully informed by a member of the research team as to the purpose of the study and the nature of the implantation procedure. The implantation procedure will be described and its potential risks and benefits will be explained in detail. Patients who voluntarily agree to participate in the trial will be asked to sign and date the written Informed Consent Form (ICF). If approved by the reviewing IRB/EC, subjects may indicate verbal, witnessed consent with the signature of a patient representative not associated with the study team if cognition is intact but the subject is unable to sign (e.g., the subject has inhibited hand function or visual disturbance).

The approved ICF must be signed for study enrollment prior to performing study related assessments. A copy of the signed and dated ICF should be provided to the subject. Subjects must be informed that they may withdraw from the study at any time, and for any reason, and will continue to receive therapy as indicated by their physician. Internet-based Case Report Forms must be completed for each subject who consents to study participation.

8.5 BASELINE ASSESSMENT: VISIT 1 (DAY 0-14) – ASSESSED DAY 14

The following information will be assessed and the documentation will be maintained as source records at the study site:

- Medical history;
- Office cuff blood pressure (Note: Office cuff BP recordings must be performed as detailed in Appendix IV);
- Check for orthostatic blood pressure and orthostatic pulse assessments;
- Daily patient diary assessments of blood pressure and medication compliance;

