13.0 STATISTICAL METHODS

Since this is a pilot study designed to evaluate the initial safety of the MobiusHD in subjects with stage 2 hypertension, no formal hypothesis testing is planned. Complete data for each study subject will be presented in an individual patient profile consisting of all CRF fields and a narrative summary. Additionally, where appropriate, descriptive statistics will be used to tabulate and summarize study outcomes. Background and demographic characteristics will be presented. Continuous variables will be summarized by descriptive statistics (sample size, mean and standard deviation, median, minimum and maximum). Discrete variables will be summarized by frequencies and percentages. Adverse events will be summarized by presenting the number and percentage of patients having any adverse event. Any other information collected (such as severity or relationship to study device) will be listed as appropriate. Any statistical tests performed to explore the data will be used only to highlight any interesting comparisons that may warrant further consideration.

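### At Days 7 and 30 the orthostatic check appears to follow a six-minute walk that is absent at baseline, so a postural drop at Day 7 cannot be told apart from an effect of the walk

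*Combined protocol and SAP*

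**What the plan says.** Before the implant, the lists for Visit 1 (Section 8.5) and Visit 2 (Section 8.6) each contain the item "Check for orthostatic blood pressure and orthostatic pulse assessments". Neither list includes a walk, and neither gives the postures.

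After the implant there are two hospital checks. Section 8.10 asks that, before release, the subject's "lying and standing bedside blood pressure should be measured and analyzed for orthostatic changes". Section 8.11 asks for a sitting-and-standing check on the day of discharge. Neither involves a walk.

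At Day 7 (Section 8.12) and Day 30 (Section 8.13) a six-minute walk test is done, and "orthostatic assessment should be done following this test". The next sentence reads "Orthostatic blood pressure measurement and orthostatic pulse assessments should be taken (sitting and standing"; it also appears in the discharge section. No rest interval is given. Table 7 ticks the walk at Days 7 and 30 only and has no orthostatic row. From Day 90 onward no orthostatic check is listed.

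The exclusion list (Section 6.2, item 11) includes "History of orthostatic hypotension". In the Synopsis, each enrollment step waits for DSMB review of 7-day data. The last unilateral step is "DSMB review of 7-day data of subjects 6-10", after which data go to FDA for the decision on bilateral implantation.

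**The concern.** The implant is meant to lower blood pressure by amplifying the baroreflex, and subjects normally stay on at least three antihypertensive drugs through month 6. A new drop on standing is therefore one of the first safety signals to look for. Because a history of orthostatic hypotension is excluded, a drop at Day 7 will tend to look new.

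If the Day 7 reading is taken just after exertion and the baseline reading was not, a difference between them has two candidate causes. A drop produced by the walk could be charged to the implant, or exertion just before the reading could mask a drop at rest. Section 11.2.3 makes relatedness depend partly on whether an event can be attributed to other procedures. Without a resting value from the same day, that judgement could be argued either way. At stake is how clearly the DSMB and FDA can read one safety measurement before subjects receive two implants.

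**Working it through.** There is no figure in the plan to reproduce. The check sets the visit sections side by side.

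| Orthostatic check | Section | Setting | Walk before it? | Postures stated |
|---|---|---|---|---|
| Visit 1 | 8.5 | before implant | no | none |
| Visit 2 | 8.6 | before implant | no | none |
| Before release | 8.10 | after implant, in hospital | no | lying, standing |
| Discharge | 8.11 | after implant, in hospital | no | sitting, standing |
| Day 7 | 8.12 | after implant, outpatient | yes (plainer reading) | sitting, standing |
| Day 30 | 8.13 | after implant, outpatient | yes (plainer reading) | sitting, standing |
| Procedure day; Day 90 onward | 8.7; 8.14 to 8.17 | – | no check listed | – |

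**Counts.** Baseline checks after a walk: 0 of 2. Outpatient post-implant checks after a walk: 2 of 2. At full enrollment and attendance this covers 20 × 2 = 40 readings, of which 10 × 1 = 10 are the unilateral cohort's Day 7 readings. None of them has a baseline reading under the same conditions.

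**What each comparison contains.** Let the measurement be the change in pressure on standing. In this single-arm study, and leaving aside any difference in posture:

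- Day 7 − Visit 2 = implant + walk + time
- Discharge − Visit 2 = early implant effect + recent procedure and hospital setting
- Day 7 − discharge = walk + time since the procedure + leaving hospital
- Day 30 − Day 7 = time only, if the walk acts equally at both visits

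No combination of these isolates the walk. The last is free of it but starts after the implant, so it says nothing about change from baseline.

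**With a resting reading added at Day 7:**

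- resting Day 7 − Visit 2 = implant + time
- post-walk Day 7 − resting Day 7 = walk, with the implant in place

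The walk drops out of the first line and is measured in the second. Time effects remain, as in any single-arm study.

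**The case against.** The strongest reply is that the plan never makes this comparison. Orthostatic pressure is not a primary, secondary or additional outcome, and Section 13.0 is descriptive, with no orthostatic change score. That stands: no stated analysis is biased. An orthostatic test is also its own control, standing against sitting at one visit. This deals with differences in pressure level, but not with a walk that alters the size of the drop.

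Second, the sentence on sitting and standing may describe a separate resting check, since identical words serve at discharge, where there is no walk. This is possible. The plainer reading is that it gives the postures for the assessment just mentioned. If a resting check was meant, its order relative to the walk is not stated and one sentence would settle it.

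Third, Appendices III, IV and VII appear by title only in the available copy. Rest intervals, postures or form labels could be there. Appendix IV is cited for office cuff pressure only, but this uncertainty stands.

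Fourth, walk-free post-implant readings exist, and discharge uses the same postures as Day 7. They belong in the safety package, but they are taken during the procedural stay and do not show the resting response a week later.

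Fifth, the post-walk check may be a deliberate provocation. That is sensible, and a resting reading beforehand makes it easier to interpret.

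**Conclusion.** The point holds as a cheap improvement to safety measurement. On the plainer reading of Sections 8.12 and 8.13, no outpatient post-implant orthostatic reading matches baseline conditions (0 of up to 40). A Day 7 drop, part of the evidence before bilateral treatment, cannot be separated from the walk. A resting value that was never taken cannot be recovered by later tabulation or from the patient profiles.

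This rests on that reading of two adjacent sentences and on the visible text. The documents give no size or direction for a walk effect, so the consequence cannot be put in mmHg or as an error rate.

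A reader might infer more than the documents support:

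- *That the primary outcome or the escalation decision is invalid.* SAEs and UADEs are counted and adjudicated however the orthostatic check is timed, and the DSMB also has the in-hospital readings and the other 7-day data.
- *That Section 13.0 is at fault for naming no orthostatic or hypotension summary.* That section is generic throughout and promises every case report form field and a narrative for each subject. With DSMB review groups of 1, 4 and 5, subject-level review is workable.
- *That hypotension and hypertension would be pooled in a table.* Section 11.3 pairs them in a list of anticipated events; it is not a tabulation scheme.

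**What to change.** At Days 7 and 30, take one sitting-and-standing blood pressure and pulse reading at rest before the walk. Keep the post-walk reading and label it as a provocation test. State the same sitting-and-standing procedure for Visits 1 and 2. Compare only the resting readings with baseline.

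The cost is at most 20 × 2 = 40 extra cuff readings at visits that already take place, slightly longer visits, and a label on the form to tell pre-walk from post-walk values. It needs a protocol amendment, which under Section 18.0 takes effect only after IRB/EC approval. If a resting check was always intended, the amendment need only say so and fix its order.

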8.18 UNSCHEDULED FOLLOW-UP VISIT

If an unscheduled follow-up visit is required, the study subject should be assessed for new or unresolved adverse events. Any testing required, including imaging studies, should be provided to the study Sponsor for DSMB adjudication. Office cuff blood pressure will be taken and assessment of the subject diary will be reviewed. Change of medications, diagnostic test results, or interventions should be documented.

8.19 SCHEDULE OF STUDY VISITS AND ASSESSMENTS

A summary of the study related assessments as outlined above is described in Table 7.

TABLE 7: SCHEDULE OF STUDY VISITS AND ASSESSMENTS

Visit	Follow-up									Long Term Follow-up
	Visit 1	Visit 2	Visit 3/ Procedure	Discharge	7 Days (+2/-3 days)	30 Days (+/- 7 days)	90 Days (+/- 14 days)	180 Days (+/- 14 days)	365 Days (+/- 14 days)	
Eligibility	✓	✓	✓							
Informed Consent	✓									
Medical History	✓									
Physical	✓		✓		✓	✓	✓	✓	✓	✓
Neurological Exam	✓		✓	✓	✓	✓	✓	✓	✓	✓
Concomitant medications	✓	✓	✓		✓	✓	✓	✓	✓	✓
Baseline 12 lead ECG	✓									
Blood Testing	✓			✓						
Patient Diary	✓	✓	✓		✓	✓	✓	✓		
Duplex Imaging		✓		✓	✓	✓		✓		
CT or MR Angiography		✓								
Renal Artery CTA/MRA or Duplex*	✓									
24 hour ABPM		✓					✓	✓		
Assessment for Carotid		✓								
6MWT					✓	✓				
MobiusHD Placement			✓							
Office cuff BP Measurement	✓	✓	✓	✓	✓	✓	✓	✓	✓	✓
Discharge				✓						
Adverse Events	✓	✓	✓	✓	✓	✓	✓	✓	✓	✓

* If not performed in the 12 months preceding screening

9.0 STUDY COMPLETION

After the subject has completed the 3-Year follow-up visit, a Subject Termination iCRF must be completed. During the course of the study, it is possible that subjects will be withdrawn from the study early. Factors leading to subject withdrawal may include, but are not limited to, the following:

- **Subject Withdrawal** - A subject may voluntarily withdraw from the study at any time without affecting his or her future medical treatment or benefits. In addition, the Investigator may withdraw a subject from the study if the subject refuses further testing or follow-up evaluations, or for any other reason as determined by the Investigator.
- **Subject Lost to Follow-Up** – If the Investigator has attempted to contact a subject at least three (3) times and receives no response, the subject may be lost to follow-up. The research staff should document at minimum three (3) attempts to contact the subject prior to terminating the subject from the trial.
- **Subject Death** - When a subject expires, the Serious Adverse Event and Subject Termination iCRFs must be completed promptly. Source documents such as death summary, autopsy report (if done), and a copy of the death certificate should be redacted of personal identifiers and provided to the designated clinical monitor and DSMB to describe the cause of the subject's death. The Investigator will notify the IRB/EC and Sponsor within 24 hours of learning of the event.

The Termination iCRF should be completed for each study subject, to record date and reason for early termination (if subject does not complete the study) or at the final visit (if subject completes all study time points).

